DIATOR

Protocol Version 2.3 07/01/2004

Study Protocol

A Randomized, Double-Blind, Placebo-Controlled, Parallel Group Study to Investigate the Effect of Atorvastatin on Residual Beta-Cell Function and Glycemic Control in Patients with Newly Diagnosed Type 1 Diabetes Mellitus

DIATOR

Diabetes Intervention with Atorvastatin

Investigational product: Atorvastatin

Indication: Newly Diagnosed Type 1 Diabetes Mellitus

Study Committee [name], [name], [name]

Principal Investigator [name]

Version: 2.3

Date: 07 September 2003

DIATOR	
Protocol Version 2.3	07/01/2004

Signature Page

I confirm that I will work according to this protocol. I will also work consistently with the ethical principles that have their origin in the Declaration of Helsinki and that are consistent with good clinical practices and the applicable laws and regulations. I will accept the monitor's overseeing of the study. I will promptly submit the protocol to applicable ethical review board(s). I confirm that if I or any of my staff are members of the ethical review board, we will abstain from voting on this protocol.

Signatures of the Study Committee [name]. med. [name] Principal Investigator Signature Date [name]. rer. nat. [name] Signature Date [name]. [name] Signature Date

DIATOR

Protocol Version 2.3 07/01/2004

Synopsis

Title A Randomized, Double-Blind, Placebo-Controlled, Parallel

Group Study to Investigate the Effect of Atorvastatin on Residual Beta-Cell Function and Glycemic Control in Patients with Newly Diagnosed Type 1 Diabetes Mellitus

DIATOR: Diabetes Intervention with Atorvastatin

Investigational product: Atorvastatin

Objectives:

 To assess the effect of atorvastatin on pancreatic beta-cell function as measured by C-peptide after a liquid mixed meal stimulation in patients with newly diagnosed type 1 diabetes mellitus

2. To assess the effect on metabolic control as measured by HbA1c and insulin requirements

3. To assess the safety and tolerability of atorvastatin in the treatment of newly diagnosed type 1 diabetes patients as indicated by adverse events, changes in physical examination, ECG, vital signs, and changes in laboratory parameters that are relevant to safety

 To assess the effect on risk factors of diabetic complications as indicated by changes in serum lipids and CRP in patients with newly diagnosed type 1 diabetes

 To assess the effect on systemic immune abnormalities in patients with type 1 diabetes mellitus as measured by effects on beta-cell autoantibodies, blood cytokines and chemokines on protein and transcriptional level

Number of patients: Up to 160 patients with recent onset type 1 diabetes

mellitus should complete all study procedures. Patients who are withdrawn from the study during the first nine

months of treatment will be replaced.

Number of study sites: About 20 study sites will participate in this trial. The

number of sites may be adjusted to assure a sufficient

number of patients can be included.

The German Diabetes Clinic will participate with

approximately 25 to 35 patients.

DIATOR

Protocol Version 2.3 07/01/2004

Efficacy endpoints:

Primary efficacy endpoint:

 Area under the C-peptide curve in a 2 hour mixed meal tolerance test after 12 months and 18 months of treatment

Secondary efficacy endpoint:

HbA1c and insulin requirements after 12 and 18 months of treatment

Study drug regimen:

starting dose 40 mg/day for 4 weeks, then increase to 80 mg/day, in case of side effects reduction to 40 mg/day

Frequency: daily, as recommended

Route: oral

Duration: 18 months

Table of contents

1	LIST	of Addreviations	8
2	lovo	estigators and Study Administrative Structure	10
_	2.1	Requirements of the Investigator(s) and Study Sites	
	2.2	Administrative Structure	10
	۷.۲	Administrative offactore	
3	Intro	oduction	12
_			
4	Stuc	dy Objectives	14
5		rall Study Design and Procedures	
	5.1	Study Design	
	5.2	Study Flow Chart	
	5.3	Study Procedures	
	5.3.		
	5.3.		
	5.3.		
	5.3.4		
	5.3.		
	5.3.0 5.3.1		
	5.5.	7 Early Discontinuation Visit	21
6	Sele	ection of Study Population	22
_	6.1	Primary Diagnosis	
	6.2	Number of Subjects	
	6.3	Inclusion Criteria	
	6.4	Exclusion Criteria	
	6.5	Withdrawal Criteria	23
7		atments to be Administered	
	7.1	Identity of Investigational Product	
	7.2	Labeling and Packaging of the Investigational Product	
	7.3	Drug Accountability	
	7.4	Blinding	
	7.5	Randomization	
	7.6	Treatment Compliance	20
8	Stuc	dy Assessments	27
_	8.1	Demographic Data	
	8.2	Medical History, including Concomitant Illnesses	
	8.3	Concomitant Medication, including insulin requirements	
	8.4	Body weight, Height and BMI	
	8.5	Vital Signs	
	8.6	Physical Examination	28
	8.7	12-Lead ECG	
	8.8	Safety Laboratory	
	8.8.	0,	
	8.8.	2 Clinical chemistry	28

8.	.8.3	Urinalysis	
8.	.8.4	Coagulation	
8.9		rum Lipids	
8.10		gnancy Test	

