5 OVERALL STUDY DESIGN AND PROCEDURES

5.1 Study Design

This study will be conducted as a randomized, double-blind, placebo-controlled, outpatient, parallel group study in adult patients with recent onset type 1 diabetes. Patients will be randomly assigned to treatment with either atorvastatin or placebo in a one-to-one manner. The treatment phase will be 18 months for each patient. Patients who are withdrawn from the study during the first nine months of the treatment phase will be replaced. A maximum of 160 patients will complete all study procedures. The number of subjects included may be adjusted following an interim analysis as specified in section 9.9)

Starting dose will be 40 mg per day of atorvastatin or a matching number of placebo tablets. After a run-in period of 4 weeks the daily dose will be increased to 80 mg per day or matching placebo. In case of side effects (e.g. myalgia) the dose will be reduced to 40 mg per day by the discretion of the investigator.

Efficacy on beta-cell preservation will be assessed by means of two-hour mixed-meal tolerance tests at baseline and after 12 months and 18 months of treatment. Safety data and data on metabolic control will be obtained at baseline and after 3, 6, 12 and 18 months of treatment.

Patients should continue insulin treatment throughout the study. A tight glycemic control should be aimed (Target HbA1c ≤ 6.5 %) from Visit 2 on.

5.2 **Study Flow Chart**

Visit	Screening	Visit 1 *	Visit 2	Visit 3	Visit 4	Visit 5	Early Discontinuation
Time	-28 to -2 days	0	3 months (±2 weeks)	6 months (± 10 days)	12 months (± 2 weeks)	18 months (± 2 weeks)	
Informed consent	х						
Inclusion/Exclusion Criteria	х						
Randomization		X					
Demographic Data	х						
Medical History and concomitant Illnesses	х						
2 h MMTT		X			х	х	
12 lead ECG	х					х	х
Vital signs	х	X	х	x	x	х	х
Body height ¹ , weight and BMI		х	х	х	х	х	х
Physical examination	х					х	x
Adverse Events		х	х	X	х	х	х
Concomitant Medication	х	х	х	х	х	х	х
Documentation of Insulin dose	Х	Х	х	х	х	х	х
Drug accountability		X	х	x	x	х	x
Hematology	х	х	х	х	х	х	х
Clinical Chemistry ¹	х	х	х	х	х	х	х
Serum Lipids	х	х	х	х	х	х	х
Coagulation	Х						
Urinalysis	х						
Transcriptional studies		х	х				
Cytokines/chemokines		Х	х		х	х	
Beta cell autoantibodies	х			х	х	х	
HCG ²	х	Х	х	х	х	х	х
Plasma CRP		х	х		х	х	
HbA1c	х	х		х	х	х	х
Fasting C-peptide		X³			X ³	X³	

Visit 1 only ²only female patients ³ sampled during mixed meal tolerance test

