9 STATISTICAL EVALUATION

9.1 Determination of sample size

For the primary endpoint the calculation of sample size is based on data on levels and variation taken from a recent study at the German Diabetes Clinic. After 12 months of intense insulin treatment, stimulated C-peptide was 0.37 ± 0.053 nmol/l (mean \pm standard deviation) With a sample size of 80 patients per group a 20% difference in stimulated C-peptide would be significant with a p-value < 0.01.

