9.9 Interim Analyses

Informal interim safety analyses will be performed at 6-monthly intervals during safety discussions between the Study Committee and the independent external Safety Review Board. Decisions will be made on the discretion of the investigators and the

Safety Review Board. Any changes to the study as a result of the data review will be made as amendments to the protocol.

In addition an interim analysis for clinical efficacy and immunology parameters will be performed after 40 percent of both treatment groups have completed Visit 4 (12 months of treatment). For this analysis the statistical methods described above will be applied.

At this interim analysis the determination of sample size may be adjusted based on the clinical efficacy data so far obtained. If a clinically relevant and statistically significant difference for the primary efficacy endpoint can be assessed at this interim analysis, the study can be prematurely stopped by the discretion of the Study Committee and the Safety Review Board.

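### The primary endpoint names months 12 and 18 without saying which decides, while the sizing and the efficacy stop run on month 12

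*Protocol*

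**What the plan says.** The Synopsis, under Efficacy endpoints, lists one primary efficacy endpoint with two times: "Area under the C-peptide curve in a 2 hour mixed meal tolerance test after 12 months and 18 months of treatment". Section 5.1 gives the two post-baseline times the same standing: "Efficacy on beta-cell preservation will be assessed by means of two-hour mixed-meal tolerance tests at baseline and after 12 months and 18 months of treatment".

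Other sections work from month 12:

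- **Section 9.1** sizes the trial for the primary endpoint from an earlier study at the lead clinic: "After 12 months of intense insulin treatment, stimulated C-peptide was 0.37" nmol/l, with SD 0.053. It gives no 18-month value.
- **Section 9.9** sets the efficacy interim after "40 percent of both treatment groups have completed Visit 4", the 12-month visit. It permits an early stop if the primary efficacy endpoint shows a clinically relevant and significant difference then. Section 13.4 repeats this as a ground for ending the study.
- **Section 9.4** defines the efficacy population after such a stop by 12 months of treatment. If there is no stop, it takes patients who complete the study, which runs 18 months.

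Sections 9.2 and 9.8 leave the choice of statistical tests to a later plan.

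**The concern.** A primary endpoint at two times needs a rule that turns two results into one conclusion. The candidate rules differ in their operating characteristics. If either time suffices, the trial has two chances of a false positive. If both must succeed, the error rate falls and power at month 18 matters. A joint analysis over time is a third option with its own properties. The protocol chooses none of them.

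The sections also pull apart. A 12-month result alone can end the trial for efficacy on the primary endpoint, so in that branch month 18 is not needed. In a trial that continues, the Synopsis gives month 18 equal primary status. If a continuing trial is significant at one time and not at the other, for example because an effect fades after month 12, the protocol does not say whether it succeeded.

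**Working it through.** **The plan's own figure.** Inputs from 9.1: mean 0.37, SD 0.053, 20% difference, 80 per group.

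- Difference: 0.20 × 0.37 = 0.074 nmol/l. Standardised: 0.074 / 0.053 = 1.40.
- t = 0.074 / (0.053 × √(2/80)) = 8.83, so p is about 2 × 10⁻¹⁵.

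The statement "With a sample size of 80 patients per group a 20% difference in stimulated C-peptide would be significant with a p-value < 0.01" is therefore true, but it does not produce 80. The same inputs need 7 to 25 per group across one- and two-sided tests at 0.05 or 0.01 with 80% to 99% power. Whether 80 is justified is a separate matter. What counts here is that the calculation has one time point, month 12.

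**Assumptions for the error rates.** The protocol states no trial alpha; its only level is the 0.01 in the sentence just quoted. I take two-sided 0.05 per test, with 0.01 as a second case. The correlation ρ between the 12- and 18-month test statistics is not given, and I take 0.5 to 0.9. Under no effect the pair (Z₁₂, Z₁₈) is bivariate normal with correlation ρ, and c = 1.96.

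- Either suffices: 1 − P(|Z₁₂| < c and |Z₁₈| < c)
- Both required: 2 × 0.05 − (either)
- Split (exactly one significant): (either) − (both)

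| ρ | Either | Both | Split |
|---|---|---|---|
| 0.5 | 9.1% | 0.9% | 8.1% |
| 0.7 | 8.3% | 1.7% | 6.7% |
| 0.8 | 7.8% | 2.2% | 5.6% |
| 0.9 | 7.0% | 3.0% | 4.1% |

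Independence gives the ceiling for either: 1 − 0.95² = 9.75%. At 0.01 per test, either gives 1.9% (ρ = 0.5) to 1.5% (ρ = 0.9).

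**Split results when the drug works.** Suppose, for illustration, 80% power at each time. Both tests are significant with probability 0.687, 0.713 and 0.750 at ρ = 0.5, 0.7 and 0.9. Exactly one is significant with probability 2 × (0.80 − both) = 23%, 17% and 10%.

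**Does ranking the times settle the error rate?** With one deciding time, or a fixed order, the two final tests together hold 5%. The interim look is a further test. With month 12 as sole primary, the interim and final statistics correlate at √0.4 = 0.632 if the interim holds 40% of the final 12-month information. Testing both at 0.05, with significance alone enough to stop, gives about 8.6%.

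**The case against.** The strongest reply is that the inflation depends on a reading the protocol never adopts. No section specifies two separate tests. Naming 12 and 18 months together can mean that both are required or that they enter one joint analysis. If both are required, the error rate is below 5%. Testing order and multiplicity are also commonly left to the statistical analysis plan, which 9.2 and 9.8 promise and which is not at hand.

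Much of this stands. A reader might infer that the false-positive rate of this trial is raised, or nearly doubled. The documents do not support that: the rise occurs only under the either-suffices rule, and at the assumed correlations it is 7% to 9%. Nor do they show that a split result would be decided after unblinding, since the later plan could supply a rule first. What the deferral does not cover is the endpoint itself. The later plan is to choose the tests, whereas the endpoint, the sizing basis and the efficacy stop are fixed in the protocol, and they do not agree.

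A second reply is that 9.1 merely borrows 12-month data and 9.9 merely times a look, while the default efficacy population in 9.4 is those who complete 18 months. That is fair. Month 12 is not designated as the deciding time, and choosing it is a design decision.

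Third, a reader might infer that requiring both times leaves the trial underpowered. On the inputs in 9.1, power at 80 per group is effectively 100%, so requiring both would cost almost nothing if month 18 had a similar effect and SD. No shortfall is shown; there is only no 18-month input.

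**Conclusion.** The point holds as an unranked two-time endpoint that conflicts with the sections acting on it. The missing decision rule and the undefined split result can be read directly from the protocol and need no numerical assumption.

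The size depends on the rule. At an assumed two-sided 0.05 per test and assumed correlations of 0.9 to 0.5, type I error is 7.0% to 9.1% if either time suffices and 3.0% to 0.9% if both are required, in each case before any interim look. The both-required reading fits poorly with 9.4 and 9.9, where 12-month data can end the trial for efficacy.

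The 8.6% for an unadjusted interim with month 12 alone is a different defect and should not be added to this one. It also treats significance as sufficient to stop. Section 9.9 asks for clinical relevance as well and leaves the decision to the two committees.

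**What to change.** - **Synopsis and 9.8:** name one deciding time point and test the other next, in fixed sequence, only if the first succeeds. The two final tests then need no alpha split between them. Month 12 matches 9.1 and the interim in 9.9.
- **9.4, if month 12 is chosen:** let the primary analysis include patients with a 12-month test who leave before month 18. The present restriction to study completers would drop them. In the same edit, reconcile the visit label: 9.4 attaches 12 months to Visit 5, while the flow chart in 5.2 has Visit 4.
- **9.9:** give the efficacy look its own alpha adjustment. Ranking the time points does not replace it.
- **Trial alpha:** state it, because every figure above depends on it.

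The cost is a few sentences in these sections and no extra patients, provided this is done before any unblinded efficacy data are seen. The real price is that, with month 12 deciding, an effect seen only at month 18 could not be claimed as the primary result. If the sponsor regards durability at 18 months as the main question, month 18 could decide instead, but 9.1, 9.4 and 9.9 would then have to be rewritten to match.

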1 LIST OF ABBREVIATIONS

ADA American Diabetes Association
ALT Alanine aminotransferase
ANOVA Analysis of variance
AP Alkaline phosphatase
AST Aspartate aminotransferase

BMI Body mass index

CD Cluster of differentiation CPK Creatine phosphokinase

CPMP Committee for Proprietary Medicinal Products

CRF Case report/record form CRP C-reactive protein ECG Electrocardiogram

GAD Glutamic acid decarboxylase

GCP Good Clinical Practice
GGT Gamma glutamyl transferase

HbA1c Glycosylated hemoglobin HCG Human chorionic gonadotropin

HDL High-density lipoprotein

HMG-CoA Hydroxy-methylglutaryl Coenzyme A IA-2 Tyrosine phosphatase (Autoantibodies)

ICA Islet cell antibody

ICAM-1 Intracellular adhesion molecule

ICH International Conference on Harmonisation

IFN Interferon IL Interleukin

INR International normalised ratio (for reporting prothrombin time)

LDH Lactate dehydrogenase LDL Low-density lipoprotein

LFA-1 lymphocyte function-associated antigen-1

MCH Mean corpuscular hemoglobin

MCHC Mean corpuscular hemoglobin concentration

MCP-1 Monocyte chemotactic protein-1 MCV Mean corpuscular volume

MHC Major histocompatibility complex MIP-1 Monocyte inflammatory protein-1

MMTT mixed meal tolerance test

NOD Nonobese diabetic

PTT Partial Thromboplastin Time SOP Standard Operating Procedure

Th1 T helper cell subset 1
Th2 T helper cell subset 2
Treg Regulatory T cell

2 INVESTIGATORS AND STUDY ADMINISTRATIVE STRUCTURE

2.1 Requirements of the Investigator(s) and Study Sites

The study will take place on an out-patient basis at about 20 study sites in Germany. The number of participating sites may be adjusted, if necessary to ensure a sufficient number of patients can be included.

Investigators will be familiar with the requirements and obligations of Good Clinical Practice. Investigators and site personnel will undergo study specific training during the site initiation.

2.2 Administrative Structure

Principal Investigator: [name]. [name]

German Diabetes Clinic D-40225 Düsseldorf

Study Committee: [name]. [name]

[name]. [name]

[name]. [name]

German Diabetes Clinic D-40225 Düsseldorf

Coordinating Center Profil Institute for Metabolic Research GmbH

D-41460 Neuss

Safety Review Board: two independent outside expert and a representative of

Profil GmbH. All members of the Safety Review Board will be physicians who will otherwise not be involved in the conduction of the study. The members of the Safety Review Board will be appointed prior to study initiation.

This study is supported by an academic grant from Pfizer GmbH, D-76032 Karlsruhe

The German Diabetes Clinic will participate with approximately 25 to 35 patients.

Profil GmbH will serve as a coordinating center and will be responsible for

- study monitoring
- participation in site selection
- training and supporting the investigators and site staff in all study related procedures
- supplying sites with study medication and study materials
- labeling, packaging, storage, shipping and disposal of study medication
- randomization procedures

- design, distribution, review and archiving of CRF-documents
- participation in the external Safety Review Board
- data management
- quality assurance
- implementation of a service as a "Central Telephone Call-Center" for the study sites
- · collection of adverse events
- 24-hour-hotline for reporting of severe adverse events.

The Safety Review Board will consist of three physicians (two outside experts and a Profil representative). Informal safety analysis will be performed 6-monthly or more frequently, if required. The Safety Review Board will take part in an interim analysis after 40 percent of all participants will have completed twelve months of treatment. Randomization code will only be broken to investigators, if necessary for reasons of safety. Decisions will be taken on the discretion of the Safety Review Board and the Study Committee .Decisions will be protocolled. Any changes to the protocol as a result of the data review will be made as amendments to the protocol.

3 INTRODUCTION

Type 1 Diabetes mellitus results from a selective destruction of the insulin secreting beta-cells of the pancreas, caused by a T-cell-mediated autoimmune process. Progressive destruction of beta-cells leads to hyperglycemia due to a lack of insulin. An imbalance in the T-cell immunoregulatory abilities plays a key role in the progression of the disease. Beta-cell destruction is enhanced by the T-helper-1 (Th1) subset of the CD4⁺ T cells and their cytokines while the T-helper-2 (Th2) subset and their cytokines have protective effects.

It has been shown that general immunosuppression (e.g. with cyclosporine) leads to a better preserved Beta-cell function (1, 2). Yet, due to the potential toxicity this approach has been discontinued in recent years.

In newer studies immunomodulators (like Anti-CD3 antibodies or a peptide from Heat shock protein -60) have been tested and have shown effects on Beta-cell-preservation (3, 4). These effects most likely result from immunomodulatory effects on Th-2/Treg activation and Th1 suppression, respectively.

Atorvastatin, which is broadly used as a lipid-lowering agent, is also a potent immunomodulator. Actually, much of its clinical benefit may be due to its property to attenuate the inflammatory component underlying atherosclerosis, metabolic syndrome and type 2 diabetes.

Statins target inflammatory responses at the level of dampening upregulation of MHC class II molecules (with an effect on T helper cell activation) or at the level of the production of inflammatory mediators such as CRP (5), but additionally by blocking the adhesion molecule LFA-1 (6). In pre-clinical trials, atorvastatin promotes a Th2 bias and reverses paralysis in central nervous system autoimmune disease (7, 8). This has already led to the initiation of a clinical trial of atorvastatin in multiple sclerosis in the USA.

The ICAM-1/LFA-1 interaction is involved in T cell migration and antigen presentation. LFA-1 interacts with the surface protein ICAM-1 on endothelial or antigen presenting cells. The latter interaction stabilizes the contact between (auto)immune helper T cells and antigen presenting cells, i.e. the immunological synapse, a well-organized site of cell-cell-interaction. Only a synapse tightly sealed by LFA-1 - ICAM-1 interactions is able to promote the activation of aggressive T helper cells of type 1 (Th1).

The Principal Investigator of the current study has done research on the interaction between ICAM-1 and its ligand for more than 10 years. Most important was his finding that the expression of ICAM-1 on immune cells is essential for the development of insulitis and diabetes in the best studied animal model of type 1 diabetes, the NOD mouse (9).

Furthermore, he discovered that soluble forms of ICAM-1, which interfere with the ICAM-1/LFA-1 interaction, can prevent diabetes onset in this animal model (Martin S, Heidenthal E, Rothe H, Schulte B, Kolb H: Soluble forms of intercellular adhesion molecule-1 intervene in the pathogenesis of autoimmune diabetes. *Diabetologia* 41: 1298-1303, 1998). For these reasons, the Principal Investigator has identified

atorvastatin as a particularly appropriate candidate for targeting immune processes involved in islet inflammation and β -cell destruction.

Further guidance come from the decision of leading experts of multiple sclerosis to do a similar trial in this debilitating immune mediated disease. It is currently believed that multiple sclerosis and type 1 diabetes share many components of etiology and immune pathogenesis.

A study in type 2 diabetic patients proved that 80 mg atorvastatin per day results in a strong decrease of high-sensitivity CRP compared to 10 mg daily or placebo. This result suggests that anti-inflammatory effects of atorvastatin might be dosedependent. (10).

In the trial described here, the effects of 80 mg atorvastatin per day on preservation of beta-cell function in recent onset type 1 diabetes will be studied, as determined by stimulated C-peptide levels. The endpoint and study population have been chosen in accordance with the guidelines for intervention trials in newly diagnosed type 1 diabetes of the Immunology of Diabetes Society (11)

